2.3 Rationale

ONC201 is a first-in-class small molecule with consistent antitumor activity in difficult-to-treat cancers as demonstrated using *in vitro*, *ex vivo*, and *in vivo* models. The mechanism of action of ONC201 appears to involve the activation of the ISR that causes a downstream inactivation Akt and ERK signaling as well as induction of the pro-apoptotic TRAIL pathway. The efficacy of ONC201 has been demonstrated in numerous solid and liquid tumor cell lines and patient sample that are refractory to chemotherapy and targeted therapies. ONC201 is effective in tumor cells harboring diverse mutations in genes such as p53, KRAS, Raf, EGFR and others that render resistance to chemotherapy and targeted therapies. Colon cancer has been selected for evaluation in this trial based on preclinical efficacy as well as the mechanism of action of ONC201 that involves engagement of the ISR, inactivation of Ras signaling, and induction of the TRAIL pathway that should be effective in these tumors based on preclinical and clinical evidence.

2.3.1 Rationale for combination of ONC201 with anti-PD1 Opdivo (Nivolumab)

The combination of ONC201 with anti-PD-1 therapy resulted in more potent *in vivo* tumor suppression with the combination versus anti-PD-1 therapy alone (Figure 15). (Wagner et al. J Clin Invest. 2018)

[figure not shown]

Figure 15. ONC201 in combination with anti-PD1. Relative tumor volume after 4 weeks in CT26 tumors in Balb/c mice treated with vehicle, 100 mg/kg ONC201, anti-PD-1, or ONC201 + anti-PD-1.

3 OBJECTIVES AND ENDPOINTS

3.1 Objectives – Phase Ib

3.1.1 Phase Ib: Primary Objective

- 2) Determine the Maximum Tolerated Dose (MTD) and/or the Recommended Phase 2 Dose (RP2D) of ONC201 when administered orally in combination with Opdivo (Nivolumab) in patients with microsatellite stable metastatic colon cancer who progressed after at least 2 lines of therapy

3.1.2 Phase Ib: Secondary Objectives

- 1) Evaluate the overall safety profile of orally-administered ONC201 in combination with Opdivo (Nivolumab) using CTCAE version 5.0.
- 2) Evaluate the pharmacokinetic (PK) profile of orally-administered agent ONC201 in combination with Opdivo (Nivolumab)
- 3) Assess the pharmacodynamic effects of orally-administered agent ONC201
- 4) Assess preliminary efficacy of ONC201 and Opdivo

3.2 Objectives – Phase II

3.2.1 Phase II: Primary Objectives

- 1) Determine progression free survival (PFS) of orally-administered ONC201 in combination with Opdivo (Nivolumab)
- 2) Determine the response rate to ONC201 in combination with Opdivo (Nivolumab), as assessed using the Response Evaluation Criteria in Solid Tumor (RECIST) version 1.1, in patients with microsatellite stable metastatic colorectal cancer

3.2.2 Phase II: Secondary Objectives

- 1) Confirm safety of phase II dose of ONC201 in combination with Opdivo (Nivolumab) using CTCAE version 5.0
- 2) Assess preliminary overall survival associated with ONC201 and Opdivo (Nivolumab) in patients with microsatellite stable metastatic colorectal cancer
- 3) Correlate clinical outcome with tumor & blood biomarkers including cancer stem cells, signaling intermediates and inhibitors, NK cells, TRAIL, granzyme, perforin, and M30.

4 STUDY DESIGN

4.1 Overview

This is a single arm Phase Ib/II, open label, safety, pharmacokinetic, pharmacodynamics and efficacy study of ONC201 in combination with Opdivo (Nivolumab) in adult patients with metastatic colorectal cancer, for whom no standard therapy is available. This study will enroll adult patients with microsatellite stable metastatic colorectal cancer who progressed after at least two lines of therapy.

4.2 Study Design

In the phase IB portion of the trial, the safety of the combination of ONC201 and nivolumab will be established in cohorts of 3-6 patients using a dose de-escalation design. Once the recommended phase 2 dose (RP2D) is determined, phase II will be initiated so a total of 34 patients will be treated at the RP2D.

Throughout the study, AEs, SAEs, laboratory values, vital signs, physical examination findings, ECOG performance status, and EKGs will be obtained to evaluate the combination treatment arms. Toxicity will be evaluated according to National Cancer Institute Common Terminology Criteria for Adverse Events (NCI CTCAE), version 5.0.

Dosing phase Ib and II:

An initial dose of ONC201 will be given -7

days prior to cycle 1, day1

Cycle = 4 weeks (28 days)

- ONC201 weekly day 1
- Nivolumab 240mg IV q2 weeks day 1 and 15 over approximately 30 minutes, with ONC201

Phase IB:

Dose de-escalation, cohorts of 3-6 patients to determine RP2D

(PK, PD, tumor biopsies)

RP2D

Phase II:

28 additional patients at RP2D

(PD and tumor biopsies)

The maximum duration of treatment will be 12 months unless it is determined that a patient would derive benefit from continued therapy beyond 12 months, as determined by the investigator. Follow-up for all patients will be approximately 6 months.

The study is expected to be completed over an approximate 3.5-year period

Archival tissue available from prior surgery or biopsy will be collected for future testing. There is a required pre-treatment biopsy which will occur post consent and prior to run-in dose of ONC-201 (D-7). A second research biopsy will be performed post cycle 2, at approximately 8 weeks and to coincide with the first imaging. If patients progress at that time they will come off study. If

the patient has not progressed, a third research biopsy will be performed at the time of progression, if progression occurs during the study treatment or follow-up time period.

Dose-limiting toxicities (DLTs) are defined below in section 6.4.2.

Serial blood samples to measure plasma concentrations of ONC201, and potentially relevant biomarkers, will be collected at pre-specified time points as indicated in the respective Schedule of evaluations table.

4.3 Number of Patients

It is anticipated that 6 evaluable patients in the Phase IB and an additional 28 patients in Phase II will be enrolled into this study. Enrollment is estimated to occur over the course of 2 years with study completion occurring over approximately 3.5 years. Because a 3 + 3 dose de-escalation design will be used, the actual sample size will depend on the number of cohorts and the number of patients enrolled in phase Ib.

4.4 Duration of Study

A cycle is defined as q 4 weeks (28 days). Nivolumab and ONC201 will start on day 1 of each cycle (following an initial dose of ONC 201 on day -7). ONC201 will be given weekly day 1, and Nivolumab will be given q 2 weeks at a flat dose of 240mg IV over an approximate 30-minute infusion. See treatment section for details.

Dosing will continue until disease progression, unacceptable toxicity per patient or treating physician, or the patient discontinues for any other reason.

The maximum duration of treatment will be 12 months unless it is determined that a patient would derive benefit from continued therapy beyond 12 months, as determined by the investigator. Follow-up for all patients will be approximately 6 months.

The study is expected to be completed over an approximate 3.5-year period

When patients discontinue study treatment, they should return to the study site 30 days (+1 week) and 100 days (+1 week) after administration of the last treatment (Nivolumab or ONC201, whichever is last) to complete the safety assessment visit and procedures.

The study will be completed in approximately 3.5 years, taking into account approximately 2 years of enrollment, 12 months of treatment and approximately 6 months of follow-up, on average.

5 ELIGIBILITY CRITERIA

5.1 Inclusion

1. Patients must have a histologically/cytologically -confirmed MSS primary colorectal adenocarcinoma tumor, with confirmation of being microsatellite stable.
2. Radiographic or clinical evidence of metastatic disease that has progressed after at least 2 prior regimens. Prior bevacizumab, cetuximab, trifluridine and tipiracil, or regorafenib is allowed, prior FOLFIRI and FOLFOX treatment is required. (Treatment with a FOLFIRINOX regimen will count as 2 regimens). Prior treatment does not have to have been in the metastatic setting.
3. Patients must have measurable disease by RECIST criteria
4. All patients must have a tumor(s) located in an area that can be biopsied as confirmed by treating physician
5. All patients must submit representative tissue from their malignancy if it is confirmed there is enough tissue from prior surgery or most recent biopsy. This can consist of archival tumor samples or tissue collected at biopsy to prove recurrence. In both cases, samples should consist of a formalin-fixed paraffin embedded (FFPE) tumor tissue block or at least 20 unstained slides (charged) of 4 μ M thickness sent to the lab address outlined in section 11.1.4. Tissue located outside of Lifespan Cancer Institute hospitals must be confirmed as requested from outside organization or that it was received from outside organization prior to enrollment.
6. All previous therapies for cancer, including radiotherapy, major surgery and investigational therapies must be discontinued for \geq 14 days before the first dose of ONC201 (D-7 run in).
7. All clinically significant adverse events related to any prior therapy must have resolved to Grade \leq 1 Common Terminology Criteria for Adverse Events (CTCAE v5.0), except alopecia or parameters defined in this eligibility list.
8. Age \geq 18 years.
9. ECOG performance status \leq 2.
10. Adequate organ and marrow function as defined below:
 - a. Absolute neutrophil count \geq 1,000/mm³ without growth factor use \leq 7 days prior to treatment (this is Day -7)
 - b. Platelets \geq 75,000/mm³ without platelet transfusion \leq 7 days prior to treatment (this is Day -7)
 - c. Hemoglobin \geq 8.0 mg/dL without red blood cell transfusion \leq 7 days prior to treatment (this is Day -7)
 - d. Total serum bilirubin \leq 1.5 X upper limit of normal (ULN)

- e. AST (SGOT)/ALT (SGPT) $\leq 2 \times$ ULN; $\leq 5 \times$ ULN if liver dysfunction is felt to be secondary to tumor burden within 14 days prior to treatment (this is Day -7)
- f. Serum creatinine $\leq 1.5 \times$ ULN (OR creatinine clearance $\geq 60 \text{ mL/min}/1.73 \text{ m}^2$) within 14 days prior to treatment (this is Day -7)
- g. Serum or urine pregnancy test (for females of childbearing potential) negative ≤ 7 days of treatment (this is Day -7)

11. Ability to understand and the willingness to sign a written informed consent document and comply with the study scheduled visits, treatment plans, laboratory tests and other procedures.
12. Women of childbearing potential (WOCBP) must agree to follow instructions for method(s) of contraception from time of consent and for the duration of study treatment through 5 months after the last dose of study treatment (ONC201 or Nivolumab, whichever is last) The decision of effective contraception will be based on the judgment of the principal investigator or a designated associate.
13. Patients must agree to the required tumor biopsies to enroll in the trial. Pre-treatment biopsies can occur any time post consent and prior to run-in ONC201 dose, a second biopsy will be required at the end of cycle 2 to assess response biomarkers, a final biopsy is included at the time of progression to assess for resistance mechanisms. Only 2 biopsies will be required for patients who initially progress at time of 2nd biopsy.

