8. Any of the following in the previous 3 months: myocardial infarction, severe/unstable angina, coronary/peripheral artery bypass graft, symptomatic congestive heart failure, cerebrovascular accident, transient ischemic attack or symptomatic pulmonary embolism as defined by treating physician.
9. Other severe acute or chronic medical or psychiatric condition or laboratory abnormality that may increase the risk associated with study participation or study drug administration, or may interfere with the interpretation of study results, or in the judgment of the investigator would make the patient inappropriate for entry into the study.
10. Participants with an active, known or suspected autoimmune disease. Participants with type I diabetes mellitus, hypothyroidism only requiring hormone replacement, skin disorders (such as vitiligo, psoriasis, or alopecia) not requiring systemic treatment, or conditions not expected to recur in the absence of an external trigger are permitted to enroll.
11. Participants with a condition requiring systemic treatment with either corticosteroids (> 10 mg daily prednisone equivalent) or other immunosuppressive medications within 14 days of day 1 of treatment. Inhaled or topical steroids, and adrenal replacement steroid doses > 10 mg daily prednisone equivalent, are permitted in the absence of active autoimmune disease
12. Patients with a history of other invasive malignancies, with the exception of non-melanoma skin cancer are excluded if there is any evidence of other malignancy being present within the last three years (2 years for invasive breast cancer). However, patients with a malignancy that is non-likely to require treatment, as per the treating physician, in the next

2 years, such as a completely resected, early stage breast cancer, or other malignancies treated with curative intent are eligible. Patients are also excluded if their previous cancer treatment contraindicates this protocol therapy.

13. Prior treatment with immunotherapy for any cancer, including immune checkpoint inhibitors or anti-CTLA4 agents
14. Participants who have received a live / attenuated vaccine within 30 days of first treatment.

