When Nivolumab and ONC201 are both due, if administration of nivolumab is delayed based on section 6.6, ONC201 may be given alone, as long as the patient meets criteria for ONC201 dosing. If it is day 1 of a cycle, please also refer to section 6.3.

Nivolumab Description

Page 43 of 145

Protocol- BrUOG 379

CONFIDENTIAL

Dates: 11/04/2018, 11/11/18, 11/16/18, 11/24/18, 11/30/18, 12/2/18, 12/6/18, 12/7/18, 12/10/18, 1/8/19 BMS review, 1/9/19, 1/13/19, 1/15/19, 1/16/19, 1/17/19, 1/20/19, 1/22/19, 2/4/19, 2/19/19, 3/19/19, AM#1 7/22/19, BMS review 8/23/19, AM#2 3/3/20, BMS approved 4/1/20, Oncoceutics approved 4/24/20, AM#3 10/26/2020, BMS approved 1/5/21, Oncoceutics approved 3/30/21

Agent	Premedications; Precautions	Dose	Route	Schedule	Cycle Length=4 weeks
Nivolumab	No premedication or hydration necessary. Subjects should be carefully monitored, as per institutional policy, for infusion reactions during nivolumab administration.	240 mg	IV over approximately 30 minutes	Day 1	Dosing: Q 14 days (2 weeks +/- 2 days) For cycle 1 day 1 a + 2 day window only is allowed

There will be no dose reductions for Nivolumab. All patients should continue to meet treatment parameters required at eligibility, unless as otherwise specified below.

Nivolumab is to be administered as an approximate 30-minute IV infusion. For details on prepared drug storage, preparation, and administration, please refer to the Nivolumab Investigator Brochure (IB). The nivolumab infusion must be promptly followed by a saline flush to clear the line of nivolumab.

Nivolumab injection is to be administered as an IV infusion through a 0.2-micron to 1.2-micron pore size, low-protein binding polyethersulfone membrane in-line filter at 240 mg. It is not to be administered as an IV push or bolus injection. Nivolumab injection can be infused undiluted (10 mg/mL) or diluted with 0.9% Sodium Chloride Injection, USP or 5% Dextrose Injection, USP to protein concentrations as low as 1 mg/mL. Care must be taken to assure sterility of the prepared solution as the product does not contain any antimicrobial preservative or bacteriostatic agent.

ONC201: dose de-escalation will proceed according to a standard 3 + 3 design. Dosing is to be given day 1 of each week and is to occur with Nivolumab dosing when each drug is to be given on the same day. There is a +/- 2-day window.

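### The protocol's only numeric hemoglobin limit is written as 8.0 mg/dL (0.008 g/dL), a level every patient exceeds, so the threshold does not function as written

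*Combined protocol and SAP*

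**What the plan says.** Section 5.1 introduces a set of laboratory limits with "Adequate organ and marrow function as defined below". Item 10c of that set requires hemoglobin of at least "8.0 mg/dL without red blood cell transfusion" during the 7 days before the Day -7 dose. The criterion therefore has two parts: a numeric threshold and a transfusion condition.

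The Appendix A checklist, which sites complete item by item and send in for registration, repeats 10c as item c with the same number and unit.

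The limit may also matter after entry. The nivolumab description in section 6.2 states: "All patients should continue to meet treatment parameters required at eligibility, unless as otherwise specified below". Footnote 8 of the section 8 schedule also requires screening laboratory results more than 14 days old at Day -7 to be repeated and to meet the eligibility criteria before treatment starts.

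**The concern.** A threshold in mg/dL is far below any hemoglobin value a patient could have, so the numeric part of 10c cannot separate eligible from ineligible patients. Because the checklist carries the same unit, the registration record does not correct the criterion.

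Two things are at stake. First, a severely anemic patient meets the numeric limit if it is read literally. Second, a site that silently substitutes a sensible unit is applying a limit the protocol does not state, so an auditor comparing a laboratory report with the criterion has no valid standard. This is an operative eligibility threshold rather than background text, which is why the unit deserves correction.

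**Working it through.** **Inputs**

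- Written limit: 8.0 mg/dL (section 5.1, item 10c; Appendix A, item c).
- Conversion: 1 g = 1,000 mg.
- Range of human hemoglobin: about 3 to 16 g/dL, from profound anemia to normal adult values. This is an assumption; the documents give no range.

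The plan does not derive the limit from anything, so there is no calculation of its own to reproduce.

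**Step 1: convert the written limit.** 8.0 mg/dL ÷ 1,000 = 0.008 g/dL (0.08 g/L).

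**Step 2: compare it with the assumed range.** Ratio = (hemoglobin in g/dL × 1,000) ÷ 8.0.

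| Hemoglobin (g/dL) | In mg/dL | Ratio to written limit | Passes as written | Passes if the same number were in g/dL |
|---|---|---|---|---|
| 3 | 3,000 | 375 | yes | no |
| 5 | 5,000 | 625 | yes | no |
| 7 | 7,000 | 875 | yes | no |
| 8 | 8,000 | 1,000 | yes | yes |
| 10 | 10,000 | 1,250 | yes | yes |
| 12 | 12,000 | 1,500 | yes | yes |
| 16 | 16,000 | 2,000 | yes | yes |

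Every value passes as written. The last column shows only what the unit does to the criterion; it is not a statement of the correct limit.

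**Step 3: look for another hemoglobin threshold.**

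- Section 6.3 (new cycle requirements) repeats the entry limits for platelets (75,000) and neutrophils (1,000), so those two can be cross-checked. It contains no hemoglobin limit.
- The hematologic dose-limiting toxicities in section 6.4.2 concern neutropenia and thrombocytopenia only.
- Inclusion 7 requires toxicity from prior therapy to have resolved to Grade 1 or less, but exempts parameters defined in the eligibility list. Hemoglobin is on that list, so residual anemia can be read as governed by 10c alone.
- Sections 6.5 and 6.6 hold treatment by toxicity grade for events attributed to a study drug. They act after entry and state no hemoglobin value.

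**Step 4: consider an extraction error.** The unit is identical in two separate places, and the neutrophil and platelet units beside it read normally. A PDF reading fault is unlikely.

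**The case against.** The strongest reply is that this is an obvious typing slip with little consequence, because other checks stand behind it:

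- The transfusion condition in 10c is unaffected and can still exclude a patient.
- Exclusion 9 in section 5.2 covers "Other severe acute or chronic medical or psychiatric condition or laboratory abnormality that may increase the risk associated with study participation", which an investigator can apply to severe anemia.
- Section 5.5 gives the central office 2 full business days to review each registration packet, and Appendix A lists the laboratory source record among the documents to send. A reviewer sees the actual hemoglobin value.

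All of this stands, and it makes enrolment of a severely anemic patient on a literal reading improbable. It does not repair the text: each of these is either a different condition or a matter of judgment, and none supplies a numeric threshold.

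A reader might infer more than the documents support:

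- **That criterion 10c excludes no one.** Only its numeric part is void.
- **That the mandatory biopsies and blood draws lose their safety gate.** The protocol presents the limit as a measure of organ and marrow function and nowhere ties it to those procedures. Where section 11.1.4 addresses hemorrhage risk from biopsy, it limits needle passes and cites no hemoglobin value.
- **That the intended limit must be 8.0 g/dL.** The per-decilitre denominator makes g/dL the likeliest intent, but 8.0 is also a possible hemoglobin value in mmol/L, and the documents do not settle the point.

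**Conclusion.** The point holds for the numeric threshold. The protocol's only numeric hemoglobin limit equals 0.008 g/dL and screens out no one. That conclusion rests on the unit conversion and on the assumption that patients' hemoglobin is of the order of 3 g/dL or more; with a margin of at least 375-fold, it is not sensitive to the exact range.

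The factor of 1,000 is conditional: it is exact if g/dL was meant. Reach into treatment is likewise only possible, because section 6.2 does not say which eligibility parameters it carries forward.

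This is a minor but genuine error in a decision threshold. Its practical effect is probably small, and no endpoint or operating characteristic of the design depends on it.

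**What to change.** The sponsor should confirm the intended hemoglobin value and unit, then correct section 5.1 item 10c and Appendix A item c together at the next amendment so that the two cannot diverge. A short memo should tell sites the confirmed limit in the meantime. The same amendment could state whether the section 6.2 sentence is meant to apply the hemoglobin limit during treatment.

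The cost is a unit correction in two places and one memo. No analysis, sample size or data collection changes.

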5.2 Exclusion

1. Patients with symptomatic brain metastases are excluded. Patients with asymptomatic and treated CNS metastases may participate in this trial. The patient must have completed any prior treatment for CNS metastases > 28 days prior to registration, including radiotherapy or surgery. Steroids for the treatment of brain metastasis are not permitted.
2. Patients with prior treatment with ONC201 or who have had prior therapy with nivolumab or with an anti-PD-1, anti-PD-L1, anti-PD-L2, anti-CTLA-4 antibody, or any other antibody or drug specifically targeting T-cell co-stimulation or immune check point pathways will be excluded
3. Active inflammatory gastrointestinal disease such as severe chronic diarrhea (unless related to underlying malignancy), gastrointestinal perforation, or intra-abdominal abscess within 6 months prior to study registration. Gastroesophageal reflux disease under controlled treatment with proton pump inhibitors is allowed.
4. Pregnant or breast feeding.
5. Current active treatment in another clinical study (treatment trial) within 14 days of D-7.

6. Uncontrolled intercurrent illness including, but not limited to, ongoing or active infection requiring IV antibiotics, hepatitis, active rheumatologic or collagen vascular disease, symptomatic congestive heart failure, unstable angina pectoris, clinically significant cardiac arrhythmia, or psychiatric illness/social situations that would limit compliance with study requirements.

NOTE: Participants with active or a history of Hepatitis B or C infection as follows:

Active hepatitis B (positive hepatitis B surface antigen [HBsAg] or hepatitis C virus (HCV) (positive HCV RNA) are not eligible to participate.

HBV carriers or those participants requiring antiviral therapy are not eligible to participate.

Participants positive for HCV antibody are eligible only if PCR is negative for HCV RNA. If PCR is positive, they are not eligible to participate.

Past HBV infection or resolved HBV infection are may be eligible on this trial provided the following criteria are met prior to randomization: Positive for hepatitis B core antibody (HBcAb), the absence of hepatitis B surface antigen (HBsAg), and no detectable HBV DNA in serum.

7. Known human immunodeficiency virus (HIV) or acquired immunodeficiency syndrome (AIDS)-related illness. (testing is not required for eligibility).
8. Any of the following in the previous 3 months: myocardial infarction, severe/unstable angina, coronary/peripheral artery bypass graft, symptomatic congestive heart failure, cerebrovascular accident, transient ischemic attack or symptomatic pulmonary embolism as defined by treating physician.
9. Other severe acute or chronic medical or psychiatric condition or laboratory abnormality that may increase the risk associated with study participation or study drug administration, or may interfere with the interpretation of study results, or in the judgment of the investigator would make the patient inappropriate for entry into the study.
10. Participants with an active, known or suspected autoimmune disease. Participants with type I diabetes mellitus, hypothyroidism only requiring hormone replacement, skin disorders (such as vitiligo, psoriasis, or alopecia) not requiring systemic treatment, or conditions not expected to recur in the absence of an external trigger are permitted to enroll.
11. Participants with a condition requiring systemic treatment with either corticosteroids (> 10 mg daily prednisone equivalent) or other immunosuppressive medications within 14 days of day 1 of treatment. Inhaled or topical steroids, and adrenal replacement steroid doses > 10 mg daily prednisone equivalent, are permitted in the absence of active autoimmune disease
12. Patients with a history of other invasive malignancies, with the exception of non-melanoma skin cancer are excluded if there is any evidence of other malignancy being present within the last three years (2 years for invasive breast cancer). However, patients with a malignancy that is non-likely to require treatment, as per the treating physician, in the next

2 years, such as a completely resected, early stage breast cancer, or other malignancies treated with curative intent are eligible. Patients are also excluded if their previous cancer treatment contraindicates this protocol therapy.

13. Prior treatment with immunotherapy for any cancer, including immune checkpoint inhibitors or anti-CTLA4 agents
14. Participants who have received a live / attenuated vaccine within 30 days of first treatment.

